| Ng | nanogram |
| PK | Pharmacokinetics |
| PP | Per-Protocol |
| RTF | rich text format |
| SAE | serious adverse event |
| SAP | statistical analysis plan |
| SAS | SAS® Software |
| SD | standard deviation |
| SE | standard error |
| TEAE | treatment-emergent adverse event |
| WHO | World Health Organization |
| WY | Woman Years |

DEFINITIONS

| | |
|--|--|
| Adverse Event (AE) | An adverse event is any untoward medical occurrence in a patient or clinical investigation subject administered a pharmaceutical product and which does not necessarily have to have a causal relationship with this treatment. An AE can, therefore, be any unfavorable and unintended sign (that could include a clinically significant abnormal laboratory finding), symptom, or disease temporally associated with the use of a medicinal product, whether or not considered related to the medicinal product. |
| Data cut-off | Includes all data with a date of occurrence up to and including the data cut-off date. |
| Modified Intent-to-Treat (MITT) Population | All subjects between 16 and 35 years of age at study entry for whom the assigned IUS is successfully placed in the uterus and for whom there is at least one assessment of pregnancy status after inserting the IUS. |
| Per-Protocol (PP) Population | A subset of the MITT population excluding subjects with major protocol deviations, to be identified prior to data cut-off. |
| Safety Population | All subjects enrolled who underwent the IUS insertion procedure, regardless of age and outcome. |
| Serious Adverse Event (SAE) | An adverse event that results in any of the following outcomes: death; life-threatening situation (subject is at immediate risk of death); inpatient hospitalization or prolongation of existing hospitalization; persistent or significant disability/incapacity; congenital anomaly/birth defect in the offspring of a subject who received study drug; important medical events that may not result in death, be immediately life-threatening, or require hospitalization, may be considered an SAE when, based upon appropriate medical judgment, they may jeopardize the subject and may require medical or surgical intervention to prevent one of the outcomes listed in this definition. |

| | |
|---------------------------------|---|
| Treatment-Emergent AE (TEAE) | AEs occurring during or after attempted IUS insertion and those pre-attempted IUS insertion existing medical conditions that worsened during the study up to the subject's last known IUS date of use or, for subjects who have discontinued, through 30 days after the subject's last known IUS date of use. |
|---------------------------------|---|

1. INTRODUCTION

This document outlines the statistical methods to be implemented during the analyses of data collected within the scope of Medicines360, Protocol M360-L102 [A Phase 3, Multi-Center, Open-Label Study of a Levonorgestrel-Releasing Intrauterine System for Long-Term, Reversible Contraception]. The purpose of this plan is to provide specific guidelines from which the analysis will proceed. Any deviations from these guidelines will be documented in the clinical study report (CSR). In the event where discrepancies in statistical analysis may be encountered between the SAP and what is described in the study protocol, the SAP will take precedence.

2. STUDY OBJECTIVES

This study is being performed to evaluate the Medicines360 levonorgestrel-releasing IUS, LNG20. LNG20 is expected to provide safe and effective contraception for up to 10 years.

2.1 Primary Objective

The primary objective of this study is to assess the efficacy of a levonorgestrel-releasing intrauterine system (LNG20) in nulliparous and parous females of child-bearing potential who request long-term, reversible contraception.

2.2 Secondary Objectives

The secondary objectives of this study are to assess:

- The safety, tolerability, bleeding patterns, and continuation rates of LNG20
- The occurrence of menses and return to fertility after IUS discontinuation
- Plasma pharmacokinetics of levonorgestrel in a subset of approximately 60 subjects with serial sampling over the duration of use
- Plasma levonorgestrel levels in a subset of 60 subjects (LNG20 16 – 35 years old arm only) following IUS removal at 121 months with sampling at various time points up to 14 days post-IUS removal
- Levonorgestrel plasma levels will be obtained for all subjects at each study visit beginning with Month 36 until Protocol Version 9 when thereafter, levonorgestrel plasma levels will be obtained in all subjects at discontinuation and also annually in all women enrolled prior to 31May2011.
- Analysis of an appropriate sampling of IUSs that are removed and, when available, expelled during the study

- The safety and tolerability of LNG20 in a small cohort of women between ages 36 and 45 years up to 8 years of use
- Endometrial thickness in a subset of 60 LNG20 16-35 year old subjects at 1 year, 5 years and 10 years

3. STUDY DESIGN AND PLAN

This is a Phase 3, open-label, multicenter evaluation of the efficacy of a levonorgestrel-releasing intrauterine system (LNG20). The original study design included a comparator group of a marketed levonorgestrel-releasing intrauterine system (Mirena) to provide comparative safety and tolerability data for European regulatory approval. The study design changed such that the Mirena group would no longer be needed for comparison; hence the recruitment of the Mirena group was terminated with 159 subjects enrolled. The data from these subjects will be used as an informative comparator only in summary demographic, medical history, adverse event incidence, vital signs, and laboratory results tables given the final Mirena group sample size.

The goals of the study include provision of information to understand efficacy and safety within the widest range of possible users of the LNG20. Typically, intrauterine contraceptive studies only include women 18-35 years of age for efficacy and safety, and place limits on parity and larger body size. Women outside of these characteristics also desire an effective intrauterine contraceptive. Accordingly, this study will include women who are both nulliparous and parous as well as women less than 18 years of age in the primary efficacy and safety analyses. Additionally, we will provide safety information on women greater than 35 years of age. Also, this study does not restrict enrollment based on weight or BMI.

Eligible subjects for the efficacy evaluation of LNG20 will include a minimum of approximately 1600 subjects 16-35 years of age using LNG20. In the original protocol, approximately 650 LNG20 and 160 Mirena subjects were randomized at a 4:1 ratio of LNG20 to Mirena. In the amended single-arm protocol currently in force, the remaining approximately 950 subjects will be assigned to LNG20 only. The 1600 LNG20 subject total represents the combined LNG20 exposure in women aged 16-35 under protocol versions 1.0 through 4.0 using the original inserter and protocol versions 5.0 and later utilizing the redesigned LNG20 inserter. Subjects in the Treatment PK substudy (approximately 60) will be assigned by the IVRS separately from the remainder of study subjects based on BMI. An additional 150 eligible females 36-45 years of age will receive LNG20 as part of a non-randomized cohort to provide additional safety and tolerability information, since IUSs are used with relative frequency by women over the age of 35.

Subjects who discontinue treatment for any reason will not be replaced.

After consent is obtained, screening procedures will be performed and eligible subjects enrolled into the trial via an Interactive Voice Response System (IVRS). Enrollment and IUS insertion may occur on the same day as the screening procedures. The assigned IUS will be inserted by a study Investigator using standardized procedures specific to each system.

LNG20 subjects will be evaluated during study treatment use for up to 85 months (Mirena subjects for up to 60 months). Study assessments will be performed at a clinic visit at Screening/Enrollment and Months 1, 3, 6, 12, 18, 24, 30, 36, 42, 48, 54, 60, 66, 72, 78, 84, 90, 96, 102, 108, 114, 120 and 121 (Mirena subjects only through Month 60 and LNG20 36-45 years old subjects only through Month 96). Telephone assessments will occur at 3 month intervals between scheduled study visits, starting at Month 9. The IUS will be removed when requested by the subject, when clinically indicated, when requested by investigator or sponsor, or at the end of 121 months of use (60 months for Mirena subjects and 96 months for LNG20 36-45 years old group).

All subjects will have a follow-up safety visit one month after discontinuing the study treatment. Additional follow-up will be conducted for subjects who:

- Have an ongoing IUS or IUS procedure-related adverse event
- Choose a non-hormonal contraceptive method or who indicate that they will attempt to become pregnant, as follows:
 - Those women who elect to start a non-hormonal contraceptive method or no contraception (including those desiring pregnancy) will be followed for return of menses or until diagnosis of secondary amenorrhea is determined
 - Those women who desire pregnancy will be followed for up to 12 months to document return to fertility

Pregnancies that occur during study treatment or after IUS discontinuation through the 30-Day Safety Follow-up Visit will be identified through subject query and urine and serum pregnancy testing. The date of conception will be confirmed by ultrasound examination for pregnancies that occur during study participation. All pregnancies with a date of conception “on treatment” (while the IUS remains in place or up to and including 7 days following IUS discontinuation) will be followed to completion and the outcome recorded.

Routine safety monitoring (including clinically indicated physical exams, adverse event assessments, and vital signs) will be conducted for all subjects. An Independent Data Monitoring Committee (IDMC) will monitor subject safety throughout study conduct, and will be sent reports of all unexpected related serious adverse events (SAEs) that may occur during the study. The IDMC will review all safety data and pregnancy rates, and make recommendations regarding study conduct.

Subjects will receive detailed instructions on how to record vaginal bleeding, dysmenorrhea, and other contraceptive use on a daily diary during the first 24 months of study participation. Thereafter, only other contraceptive use will continue to be recorded daily on a diary for the remainder of study treatment in addition to the information collected at each study visit. After 24 months, bleeding and dysmenorrhea information will be obtained for the remainder of study treatment via interviews by study staff during each study follow-up visit and contact (every 3 months) during treatment.

In addition, levonorgestrel plasma levels will be obtained for all subjects every 6 months and at IUS discontinuation beginning with Month 36 until Protocol Version 9 when thereafter, levonorgestrel plasma levels will be obtained in all subjects at IUS discontinuation and also annually in all women enrolled prior to 31May2011.

The Sponsor intends to retain all IUSs that are removed or expelled (when possible) and analyze an appropriate sample of these systems.

The following substudies will be performed at selected sites:

- Levonorgestrel PK data will be obtained in a subset of approximately 60 subjects (20 non-obese LNG20 subjects, 20 non-obese Mirena subjects and 20 obese LNG20 subjects). LNG plasma samples will be obtained at Enrollment (pre-IUS insertion), Weeks 1 and 2, and Months 1, 3, 6, 9, 12, 18, 24, 30 or Early Discontinuation after IUS insertion (includes three extra visits at Weeks 1 and 2, and Month 9, not included in the main study). These subjects will be required to give informed consent for participation in the levonorgestrel PK subset
- A subset of 60 subjects assigned to LNG20 and completing 121 months of study treatment will have levonorgestrel samples obtained at various time points after IUS removal to characterize the LNG elimination profile. Each subject in this subset will be randomized to one time point (one extra visit) post-IUS removal (24 hours, 48 hours, 7 days or 14 days) such that fifteen subjects are randomized to each time point

- A subset of 60 women assigned to LNG20 at selected sites will have transvaginal ultrasound evaluations at enrollment (pre-IUS insertion), one year, five years and ten years (pre-IUS removal) to assess changes in endometrial thickness

5. GENERAL ANALYSIS CONSIDERATIONS

5.1 Data Summaries

Summary tables, figures, and data listings will be used to report the efficacy and safety outcomes for this study. Continuous variables will be summarized with means, standard deviations, medians, minimums, and maximums. Categorical variables will be summarized by counts and by percentage of subjects in corresponding categories. No formal statistical testing of any kind will be performed for this study.

Efficacy summaries consisting of the Pearl Index point estimate and its 95% confidence interval will be limited to the LNG20 16-35 year old study population, and the principal calculation based on all 28-day cycles of use where no other birth control method was reported. Subgroup assessments of pregnancy outcomes by *a priori* defined criteria, e.g., BMI, will be presented for the LNG20 16-35 year-old and LNG20 36-45 year-old study populations. Safety summaries will include the LNG20 16-35 year-old, LNG20 36-45 year old, and Mirena study populations. Depending on the safety endpoint of interest, the LNG20 study populations may be presented as a pooled sample of all subjects exposed to LNG20.

Individual subject data obtained from the case report forms (CRFs), pharmacokinetic data, and any derived data will be presented by treatment group and subject in data listings. This will include subject-level data listings by site as described [REDACTED]

[REDACTED]
[REDACTED]
that include derived data fields (e.g., estimates for missing adverse event onset dates) will include the original reported data and the derived value.

All forms of output described in this plan or any amendment that follows prior to any database cut-off for analyses or final database lock are considered *a priori* considerations. Any analyses performed subsequent to database cut-off or final database lock will be considered post-hoc and exploratory. Post-hoc analyses will be identified in the CSR.

All analyses and tabulations will be performed using SAS® Version 9.3 or higher. Pharmacokinetic analyses will be performed using Phoenix® WinNonlin® Version 6.4. Tables, figures, and listings will be presented in RTF/DOC (MS Word-readable) format. Upon completion, all SAS programs will be validated by an independent programmer. In addition, all program output will undergo a senior level statistical review. The validation process will be used to confirm that statistically valid methods have been implemented and that all data manipulations and calculations are accurate. Checks will be made to

ensure accuracy, consistency with this plan, consistency within tables, and consistency between tables and corresponding data listings. Upon completion of validation and quality review procedures, all documentation will be collected and filed by the project statistician or designee.

5.2 Data Handling

5.2.1 Conventions

Percentages will be based on available data, and denominators will generally exclude missing values.

The precision of the original measurements will be maintained in summaries and listings, when possible. Generally, means, medians and standard deviations will be presented with an increased level of precision as follows: means and medians will be presented to one more decimal place than the raw data, and the standard deviations will be presented to two more decimal places than the raw data.

Summaries of continuous variables that have some values recorded using approximate values (e.g. < or >) will use imputed values. The approximate values will be imputed using the closest exact value for that measurement. Listings will present the data in the original format.

For tables where rounding is required, rounding will be done to the nearest round-off unit. For example, if the round-off unit is the ones place (i.e., integers), values $\geq XX.5$ will be rounded up to $XX+1$ while values $< XX.5$ will be rounded down to XX .

For frequency counts of categorical variables, categories whose counts are zero will be displayed for the sake of completeness. For example, if none of the subjects discontinue due to “lost to follow-up,” this reason will be included in the table with a count of 0. Categories with zero counts will not have zero percentages displayed.

5.2.2 Unscheduled Visits

Unscheduled visits will be used in the determination of baseline value when applicable, but will otherwise only be listed in the applicable data listings.

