- Pap test if indicated, see section 6.11
 - All subjects: Months 12, 24, 36 and 48
 - All LNG20 subjects: also Months 60, 72, 84
 - LNG20 16-35 year old enrollment group: also Months 96, 108 and 120
- STD testing:
 - Chlamydia testing for all subjects 25 years old or younger
 - All subjects: Months 12, 24, 36 and 48
 - All LNG20 subjects: also Months 60, 72, 84
 - LNG20 16-35 year old enrollment group: also Months 96, 108 and 120
 - Chlamydia and gonorrhea testing for any subject following a change in sexual partner since the last study visit. In addition HIV and any other appropriate STD testing should be performed as recommended by the CDC.
- Interview subject regarding future plans for relocation or discontinuation
- Month 90 visit for LNG20 36-45 year old enrollment group and Month 120 visit for LNG20 16-35 year old enrollment group: Discuss contraception options in preparation for the upcoming Discontinuation Visit such that the subject can immediately initiate another method (the site should attempt to have her desired method available) or be abstinent to:
 - Avoid conception within 7 days after IUS discontinuation
 - Enable the subject to avoid undesired pregnancy
- Schedule next appointment

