6.5 Contacts Between Study Visits

Telephone or e-mail contacts for safety evaluation will occur at the end of 9, 15, 21, 27, 33, 39, 45, 51, 57, 63, 69, 75, 81, 87, 93, 99, 105, 111 and 117 months of use (LNG20 36-45 year old enrollment group only through Month 93 and Mirena subjects only through Month 57). The contacts should occur within 14 days before or after the expected contact date.

- Review of adverse events or changes in medical history
- Review of concomitant medications
- Review contraception method history since last scheduled study contact. The IUS would be considered to be her primary method of contraception if no regular use of other contraception is indicated on the diaries.
- Complete Bleeding/Cramping Form
 - All subjects: Months 27, 33, 39, 45, 51 and 57
 - All LNG20 subjects: also Months 63, 69, 75, 81, 87, 93
 - LNG20 16-35 year old enrollment group: also Months 99, 105, 111 and 117
- Inquire about change in sexual partner. If a contact elicits that there has been a change in sexual partner since the last time the subject had STD testing, she should be asked to come to the office for an Unscheduled Visit for Chlamydia and gonorrhea testing. In addition, HIV and any other appropriate STD testing should be performed as per CDC recommendations.
- Interview subject regarding future plans for relocation or discontinuation
- LNG20 subjects who are beyond the Month 90 study visit at the time that an investigative site obtains Institutional Review Board approval of Protocol Version 9.0 will be informed about the amendment changes at the Month 93 telephone contact or, if the Month 93 telephone contact has already occurred, at an additional telephone contact.

- Telephone contact prior to any early IUS discontinuation:
 - Discuss contraception options in preparation for the upcoming Discontinuation Visit such that the subject can immediately initiate another method (the site should attempt to have her desired method available) or be abstinent to:
 - Avoid conception within 7 days after IUS discontinuation
 - Enable the subject to avoid undesired pregnancy
 - Request the subject not have intercourse for at least 24 hours before the Discontinuation Visit; the visit may need to be rescheduled if the subject has intercourse within 24 hours of IUS removal
- Confirmation of next scheduled appointment

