6.13 Management of Unevaluable Testing During the Study

An unevaluable test is any test for which the laboratory received a sample or specimen but could not produce a result.

- Screening Visit Tests
 - If appropriately collected prior to enrollment and results reported after successful IUS insertion, it is not a protocol deviation
 - Repeat testing should occur as follows:
 - If screening and enrollment are not scheduled on the same day, the unevaluable tests should be repeated *prior* to enrollment
 - If screening and enrollment occurred on the same day, or successful insertion occurred prior to obtaining the test results, the unevaluable tests should be repeated as follows:
 - hemoglobin, serum creatinine, AST, ALT, or bilirubin: next study visit (second IUS insertion attempt, or Month 1 as applicable)
 - Chlamydia and/or gonorrhea: as soon as possible (as an Unscheduled Visit or at the next scheduled visit, if an unscheduled visit is not possible)
- Non-Screening Visit Tests
 - Pap test: repeat at next study visit
 - Chlamydia and/or gonorrhea, hemoglobin, or quantitative hCG: repeat as soon as possible (as an Unscheduled Visit)

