Counsel HIV/STD Risks	X			X							
Review Diary Compliance		X	X	X	X	X	X	X	X	X	
Bleeding/Cramping Form					X	X	X	X	X	X	X
Review Contraception Use ¹⁰	X	X	X	X	X	X	X	X	X	X	
Sexual Partner Status ¹¹		X	X ¹¹	X	X	X	X ¹¹	X	X ¹¹	X	
Review of Adverse Events	X	X	X	X	X	X	X	X	X	X	X
Review Concomitant Meds	X	X	X	X	X	X	X	X	X	X	X
Plasma Levonorgestrel					X		X			X ¹¹	
Verify IUS Presence ¹¹		X		X	X	X		X		X	
Removal of IUS										X	
Ask About Relocation or Early Discontinuation Plans		X	X	X	X	X	X	X			
Contraception Counseling									X ¹⁴	X ¹⁶	X
Schedule/Confirm Next Visit	X	X	X	X		X	X	X	X	X	X ^{16,17}

¹ To occur ±14 days of scheduled Month (±7 days for Months 1 and 3)² Medications for 7 days prior to enrollment and anticoagulants for 30 days³ Include any clinically indicated physical exam⁴ Pap test per protocol section 6.11 guidelines⁵ Chlamydia testing for all subjects ≤ 25 years old⁶ Both tests if change in sexual partner since last tested or last visit⁷ If not tested within the previous 6 months⁸ Urine pregnancy if not done on same day prior to insertion⁹ Includes creatinine, AST, ALT, bilirubin¹⁰ Review other contraception use¹¹ If change in sexual partner is noted during contact bring in for unscheduled G/C testing prior to next clinic visit¹² Not required if Early Discontinuation <36 months¹³ By palpation or visualization (ultrasound evaluation if missing strings at first and annual visits)¹⁴ For contact prior to Month 84 Term/ED discuss contraception options for discontinuation visit¹⁵ Initiation of primary method of contraception when possible¹⁶ Appropriate monthly contact by phone or clinic visit to follow ongoing AEs and return to menses. If no return to menses within 3 months of IUS removal/expulsion, refer for evaluation and continue follow-up until diagnosis is made¹⁷ For women desiring pregnancy follow by phone contact every 3 months up to one year

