11.13.2 Chlamydia and Gonorrhea Evaluations

The frequency and percentage of Chlamydia and gonorrhea results will be summarized for each applicable visit by treatment group. Similar to hemoglobin analyses, if a baseline value is not obtained due to protocol deviation or laboratory error, a Month 1 visit or an Unscheduled Visit within the Month 1 visit window will be used as Baseline in a sensitivity analysis. In addition, the frequency and percentage of subjects with a change in sexual partners will be summarized.

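### Post-baseline unscheduled Chlamydia and gonorrhea results, and repeats of unevaluable tests, are listed but never tabulated, although the protocol requires them to be obtained at Unscheduled Visits

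*SAP*

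**What the plan says.** SAP 5.2.2 sets one rule for all unscheduled data: "Unscheduled visits will be used in the determination of baseline value when applicable, but will otherwise only be listed in the applicable data listings".

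SAP 11.13.2 describes the infection-test table: "The frequency and percentage of Chlamydia and gonorrhea results will be summarized for each applicable visit by treatment group". Its only provision for unscheduled results concerns a missing baseline: "an Unscheduled Visit within the Month 1 visit window will be used as Baseline in a sensitivity analysis". SAP 11.13.1 summarizes hemoglobin at Baseline, Month 12, Month 60 and the Final Visit, with the same baseline exception.

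The protocol gives Unscheduled Visits a defined role in testing:

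- Section 6.5: if a contact shows a partner change since the last STD testing, "she should be asked to come to the office for an Unscheduled Visit for Chlamydia and gonorrhea testing".
- Appendix A repeats the instruction: "If change in sexual partner is noted during contact bring in for unscheduled G/C testing prior to next clinic visit".
- Section 6.13, for non-screening tests that could not be evaluated: "Chlamydia and/or gonorrhea, hemoglobin, or quantitative hCG: repeat as soon as possible (as an Unscheduled Visit").
- Section 6.4, at scheduled clinic visits: "Chlamydia and gonorrhea testing for any subject following a change in sexual partner since the last study visit". Section 6.6 asks for the same at discontinuation.

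SAP Section 1 gives the SAP precedence over the protocol on analysis.

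**The concern.** Results obtained because the protocol requires them, at the visit type it prescribes, go into listings only. Chlamydia has a routine annual follow-up test only for women aged 25 or younger. Gonorrhea has no routine follow-up test, so almost all planned follow-up gonorrhea testing is prompted by partner change. Part of that testing falls outside the table.

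SAP 11.13.2 also summarizes the proportion of women with a change in sexual partner. Changes reported at contacts can be counted there while the tests they prompted are left out of the same section.

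At stake is the completeness of a descriptive safety table that bears on a risk named in Protocol 7.1.4. For hemoglobin, a valid value obtained as instructed would be treated as missing.

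**Working it through.** **Which results are tabulated**

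| Result | Where obtained | Treatment under the SAP |
|---|---|---|
| Partner change first reported at a clinic visit | That visit (Protocol 6.4, 6.6) | Tabulated |
| Partner change first reported at a contact | Unscheduled Visit (6.5, Appendix A) | Listed only |
| Repeat of an unevaluable follow-up Chlamydia, gonorrhea or hemoglobin test | Unscheduled Visit (6.13) | Listed only |

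The omission therefore depends on where the change was first reported, and on whether the first specimen could be evaluated.

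**Size of the omitted share**

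The documents give no figure to reproduce, so this is an estimate from the calendar.

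Inputs:

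- Contacts (Protocol 6.5) fall at "9, 15, 21, 27, 33, 39, 45, 51, 57, 63, 69, 75, 81, 87, 93, 99, 105, 111 and 117 months of use" in the LNG20 16-35 group: (117 - 9)/6 + 1 = 19. The LNG20 36-45 group stops at Month 93: (93 - 9)/6 + 1 = 15. Mirena stops at Month 57: (57 - 9)/6 + 1 = 9.
- Each contact comes 3 months after the preceding clinic visit, so it is the first inquiry for changes in those 3 months.
- Treatment lasts 121, 96 and 60 months (Protocol 6.6).
- Discontinuation of 20%, 19% and 17% in years 1 to 3, then 16% per year (Protocol 9.1, SAP 4), is used only to weight the months.

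Assumptions: a constant rate of partner change, full attendance at the Unscheduled Visit, and no second test at the next clinic visit. The share is then f = 3 × contacts / months of treatment.

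| Group | f | Weighted by discontinuation |
|---|---|---|
| LNG20 16-35 | 57/121 = 47.1% | 45.5% |
| LNG20 36-45 | 45/96 = 46.9% | 45.1% |
| Mirena | 27/60 = 45.0% | 43.4% |

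*Attendance.* Suppose a fraction a of the women asked attend and the others are tested at the next clinic visit. The share is then a × f. For LNG20 16-35 it is 0.75 × 47.1% = 35%, 0.50 × 47.1% = 24%, and 0.25 × 47.1% = 12%.

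*Retest.* The trigger in 6.4 can be read as requiring another test at the next clinic visit. Each change then yields one tabulated test, and a fraction f yields an unscheduled test as well. The share is f/(1 + f) = 0.471/1.471 = 32%. The documents do not settle which reading applies: 6.4 refers to the last study visit, 6.5 to the last STD testing, and Appendix A to either.

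**Effect on the table**

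- *Count of positive tests.* A positive result at an Unscheduled Visit adds nothing to the table, so the count can only be too low or unchanged.
- *Percentage positive.* Let s be the omitted share of all tests, and p_out and p_in the positivity of omitted and tabulated tests. The full percentage minus the tabulated one is s × (p_out - p_in). The documents give neither positivity, so the sign is unknown.
- *Hemoglobin.* If the Month 12 or Month 60 specimen cannot be evaluated, the valid repeat is listed only. SAP 5.3 does not impute, and under 5.2.1 denominators generally exclude missing values, so the woman drops out of that summary. The number affected cannot be estimated from the documents.

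**The case against.** The strongest reply is that infections are reported elsewhere. Protocol 6.12 has positive Chlamydia and gonorrhea tests treated. Section 7.11 counts a finding that needs therapeutic intervention as clinically significant and requires it to be recorded as an adverse event if it meets that definition. SAP 11.2 summarizes TEAEs by preferred term without regard to visit type. Protocol 9.8 gives special attention to uterine and other urogenital infections. Keeping off-schedule results out of by-visit tables is also a common convention.

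Much of this stands. It limits the gap to the test-result tables and makes it likely that treated infections are visible. It does not close the gap: TEAE incidence uses the whole Safety Population as denominator (SAP 11.2), so it shows neither how many women were tested nor how many tests were positive. It also does nothing for the hemoglobin repeats.

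A reader might go further and infer three things that the documents do not support:

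- *That tests prompted by a new partner are excluded as a class, so the table omits about half of the highest-risk tests.* Partner-change tests at scheduled visits stay in. Nearly half is the upper end and needs all three assumptions above. The documents give no ranking of tests by risk.
- *That the percentage positive is biased downward.* This needs higher positivity in the omitted tests, which is not shown. By Month 120 even a woman who entered at 16 is 26, so planned Chlamydia tests at that visit, tabulated or not, are partner-change tests.
- *That infection reporting as a whole is incomplete.* The TEAE route argues against this.

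**Conclusion.** The SAP rule and the protocol's testing route conflict. If SAP 5.2.2 is followed as written, the Chlamydia and gonorrhea table omits part of the partner-change testing and all repeats of unevaluable follow-up tests done at Unscheduled Visits. The count of positive tests is understated whenever one of those results is positive. Valid repeat hemoglobin values for Months 12 and 60 are lost as well.

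The omitted share of partner-change tests is at most about 43-47%, and smaller with retesting or incomplete attendance: about 32% and about 12% in the cases worked above. All of these rest on a constant rate of partner change, which the documents neither state nor contradict.

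The effect is confined to descriptive safety tables. The Pearl Index is untouched, because SAP 9.1 defines pregnancy by any reported positive urine or blood test, whatever the visit type. The point merits a correction because the results are required and the remedy is small.

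**What to change.** Amend SAP 5.2.2, 11.13.1 and 11.13.2 before the next data cut-off:

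1. Assign each post-baseline unscheduled Chlamydia or gonorrhea result to the interval ending at the next scheduled clinic visit, and define the applicable visit accordingly.
2. For each interval, report the number of women tested and the number with any positive result. A woman tested more than once in an interval counts once, as positive if any result is positive. This works whether or not she is tested again at the clinic visit.
3. Add the cumulative number of women with any positive test during use.
4. Use a valid repeat of an unevaluable Chlamydia, gonorrhea or hemoglobin test as the result for the visit it replaces, not for the following interval.

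A split by reason for testing is not proposed, because the documents do not show that the reason is recorded for each test.

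The cost is SAP wording and minor reprogramming. Sites already enter laboratory values in the database (Protocol 8), and the SAP already lists unscheduled results. The downside is that more positive results may be reported.
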